13.2 Sample Size/Accrual Rate

13.2.1 Sample Size

A maximum of 96 evaluable patients (48 in each group) will be accrued unless undue toxicity is encountered. We anticipate accruing an additional 10 patients to account for ineligibility, cancellation, major treatment violation, or other reasons. Maximum projected accrual is 106 patients.

13.2.2 Accrual Rate and Study Duration

The anticipated accrual rate is approximately 5-6 patients per month. Therefore, the accrual period for this phase 2 study is expected to be about 20 months. The final analysis can begin approximately 26 months after the trial begins, i.e. as soon as the final patient accrued to this trial has been followed for at least 6 months.

13.2.3 Inclusion of Women and Minorities

This study will be available to all eligible patients, regardless of race, gender or ethnic origin.

There is no information currently available regarding differential effects of this regimen in subsets defined by race or gender, and there is no reason to expect such differences to exist. Therefore, although the planned analysis will, as always, look for differences in treatment effect based on racial and gender groupings, the sample size is not increased in order to provide additional power for subset analyses.

Based on prior studies involving similar disease sites, we expect about 30-35% of patients will be classified as minorities by race and about 40% of patients will be women. Expected sizes of racial by gender subsets are shown in the following table:

Racial Categories	Not Hispani	c or Latino	Hispanic	Total	
	Female	Female Male Fem		Male	
American Indian/ Alaska Native	0	1	0	0	1
Asian	2	3	0	0	5
Native Hawaiian or Other Pacific Islander	0	1	0	0	1

PLANNED ENROLLMENT REPORT

Racial Categories	Not Hispani	c or Latino	Hispanic	Total	
	Female Male		Female	Male	
Black or African American	5	8	0	0	13
White	30	44	4	5	83
More Than One Race	1	1	0	1	3
Total	38	58	4	6	106

13.3 Stratification Factors

- 13.3.1 Age group: < 65 years or ≥ 65 years
- 13.3.2 Previous autologous stem cell transplant: yes vs. no
- 13.3.3 Diagnosis category (per section 3.1.1): Category A vs. Category B

13.4 Analysis of Secondary Endpoints

13.4.1 Duration of Response

Duration of response is defined for all evaluable patients who have achieved a response as the date at which the patient's objective status is first noted to be a PR or CR for patients evaluated by CT-based criteria or CMR or PMR for patients evaluated by PET-CT based criteria to the earliest date progression (PMD or PD) is documented. If a patient has not had disease progression, they will be censored on the date of their last disease assessment. The distribution of duration of response will be estimated using the method of Kaplan-Meier. The comparison of duration of response between two treatment arms will be based on the log-rank test.

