5.4 Duration of Follow Up Following End of Therapy

Patients will be followed for additional 100 days (based on 5 half-lives) after end of therapy or until death, whichever occurs first. Patients removed from therapy for unacceptable adverse event(s) will be followed until resolution or stabilization of the adverse event.

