11.1.3 Schedule of Evaluations

PET/CT scans are required at baseline for all patients. Repeat PET-CT scans should be obtained every 12 weeks unless otherwise clinically indicated.

Definitions for clinical response for patients with lymphoma are based on the lymphoma response to immunomodulatory therapy criteria or LYRIC (Cheson *et al.*, 2016). Lymph node measurements should be taken from the CT portion of the PET/CT, or other dedicated CT scans where applicable. Measurement of lymphadenopathy for purposes of assessing for PR will be determined by adding the sum of the products of the maximal perpendicular diameters of measured lesions (SPD). The perpendicular diameter of a single node is sufficient to evaluate for PD (see Table 11.1.4). Measurable extranodal disease should be assessed in a manner similar to that for nodal disease. For these recommendations, the spleen is considered nodal disease. Disease that is only assessable (*e.g.*, pleural effusions, bone lesions) will be recorded as present or absent only, unless, while an abnormality is still noted by imaging studies or physical examination, it is found to be histologically and pathologically negative.

For response assessment, PET-CT is preferred for staging of FDG-avid lymphomas and CT scan is preferred in the other lymphomas

Progressive disease is based on either PET-CT based (PMD) or CT based (PD) response criteria. Definition of progressive disease according to LYRIC is same as the Lugano classification except that a new category of indeterminate response (IR) is added. Patients whose disease fall in the IR category may continue treatment for additional 12 weeks if the patient remains clinically stable as judged by the treating physician. A repeat imaging

study in 12 weeks (or earlier if clinically indicated) is mandatory to confirm or refute disease progression. PET confirmation of progressive disease is per physician discretion.

11.1.4 Lymphoma Response to Immunomodulatory Therapy Criteria [LYRIC] (adapted from Cheson *et al.*, 2016)

	PET-CT Based Response	CT-Based Response
Complete Response (CR)	Complete metabolic response (CMR)	Complete radiologic response (CR) (all of the following)

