Final Decision Rule: The final analysis will take place after all 48 evaluable patients in each group have been followed for at least 6 months. The response rates will be compared between the two groups using Fisher's exact test. If the response rate is higher in Group 2 the experimental group, where the p-value < 0.15, this will be considered sufficient evidence that Group 2 the experimental group may be recommended for further testing in subsequent studies. Otherwise, we will conclude that there is not statistical evidence of superiority of the experimental regimen.

Over Accrual: If more than the target number of patients are accrued, the additional patients will not be used to evaluate the stopping rule or used in any decision making process however, they will be included in final point estimates and confidence intervals.

NOTE: The trial will not be halted while the first 24 patients in each group are evaluated for the interim analysis. However, if the accrual is especially rapid, we may temporarily suspend accrual to prevent missing important acute toxicity patterns.

Other Considerations: Toxicity, quality/duration of response, and patterns of treatment failure observed in this study, as well as scientific discoveries or changes in standard care will be taken into account in any decision to terminate the study.

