13.4.3 Progression Free Survival

Progression free survival is defined as the time from randomization to the earliest

date of documentation of disease progression (PMD or PD) or death due to any cause. The distribution of progression-free survival will be estimated using the method of Kaplan-Meier. The comparison of progression-free survival between two treatment arms will be based on the log-rank test.

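### Duration of response censors deaths and is log-rank tested in responders only, so it measures time to progression among responders and is not a randomised comparison

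*Combined protocol and SAP*

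**What the plan says.** Duration of response is a secondary objective (section 1.2.2). Section 13.4.1 restricts it to responders: "Duration of response is defined for all evaluable patients who have achieved a response". The clock runs from the first PR, CR, PMR or CMR to the first documented PD or PMD. Death is not listed as an event, and the censoring rule covers everyone else: "If a patient has not had disease progression, they will be censored on the date of their last disease assessment". The section closes: "The comparison of duration of response between two treatment arms will be based on the log-rank test". It gives no significance level, no sidedness and no statement that the comparison is descriptive.

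Section 13.4.3 treats the same event differently. Progression-free survival runs from randomisation to the earliest "date of documentation of disease progression (PMD or PD) or death due to any cause".

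Three other places bear on the point:
- Section 13.1.3, in its paragraph on other considerations, names "Toxicity, quality/duration of response, and patterns of treatment failure observed in this study" among the matters weighed in any decision to terminate the study.
- Section 11.1.3 sets the imaging schedule: "Repeat PET-CT scans should be obtained every 12 weeks unless otherwise clinically indicated".
- Section 5.4 sets follow-up after treatment: "Patients will be followed for additional 100 days (based on 5 half-lives) after end of therapy or until death, whichever occurs first".

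**The concern.** There are two separate faults.

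First, a responder who dies without documented progression leaves the analysis at the last scan, as though nothing further were known. The Kaplan-Meier curve then estimates time to progression in a setting where death does not happen. Most readers will take it as how long responses last, and read that way it is too long whenever such deaths occur. An arm with more of them is not penalised, although the rule does not by itself lengthen that arm's curve. In relapsed aggressive lymphoma with scans 12 weeks apart, death before documented progression is plausible.

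Second, the log-rank test compares patients chosen by their response. If the combination works, its responders include patients who would not have responded to nivolumab alone. The two responder groups then differ for reasons other than the effect of treatment on durability, and the p-value can point against a combination that harms nobody, or flatter one.

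At stake are the durability estimate, a secondary p-value, and an input to any discussion of stopping the study.

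**Working it through.** **The plan's own figure.** Section 13.1.3 states 80% power with 48 per group, response rates of 25% and 45%, and one-sided 0.15. Exact enumeration of the one-sided Fisher test (p < 0.15) gives 80.9%, so the figure reproduces. It concerns response rate; the plan states no figure for duration of response.

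**Inputs from the documents.** 48 per group, 25% and 45% (13.1.3); accrual of about 20 months and final analysis at about 26 months (13.2.2); scans every 12 weeks, or 2.76 months (11.1.3).

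**Assumptions.** Exponential times, uniform accrual, response dated at week 12, deaths independent of progression. All median durations and death shares below are assumed.

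**Step 1: responders.** 48 × 0.25 = 12 and 48 × 0.45 = 21.6, together 33.6, or about 34.

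**Step 2: events.** Take a median time to progression or death of 6 months, so the hazard is ln 2 / 6 = 0.1155 per month. Follow-up after response runs uniformly from 26 − 20 − 2.76 = 3.24 to 26 − 2.76 = 23.24 months. The fraction without an event is (e^(−0.1155 × 3.24) − e^(−0.1155 × 23.24)) / (20 × 0.1155) = (0.688 − 0.068) / 2.31 = 0.268. Expected events are 0.732 × 34 = 24.9. Deaths at 5% to 30% of these would be 1.2 to 7.5, roughly 1 to 7 patients.

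**Step 3: effect of censoring deaths.** If a share s of first events are deaths without documented progression, the progression hazard is (1 − s) times the total hazard. The reported median is then 6 / (1 − s).

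| s | Death counted (months) | As written (months) |
|---|---|---|
| 0% | 6.0 | 6.0 |
| 5% | 6.0 | 6.3 |
| 10% | 6.0 | 6.7 |
| 20% | 6.0 | 7.5 |
| 30% | 6.0 | 8.6 |

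A simulation of 400,000 responders under the trial's accrual gave 5.99, 6.32, 6.67, 7.52 and 8.51 months for the rule as written.

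If instead the progression median is held at 6.0 and deaths are added as 10%, 20% or 30% of first events, the reported median stays at 6.0. The death-inclusive median, 6 × (1 − s), falls to 5.4, 4.8 or 4.2.

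If progression can be dated only at the 12-weekly scan, medians move in steps. There is no shift when 6% to 12% of observed first events are deaths. At 24% the rule as written gives 8.3 months against 7.5, and at 35% it gives 11.0 against 6.7.

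**Step 4: effect of selection.** Suppose the 25% who would respond on either arm have a median duration of 9 months, and the further 20% respond only to the combination. With 20,000 simulated trials per case and an illustrative one-sided 0.15 test in each direction:

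| Median in added responders (months) | Average hazard ratio, responders only | Result |
|---|---|---|
| 9 (no difference) | – | called worse in 15% |
| 8 | 1.05 | called worse in 17% |
| 7 | 1.11 | called worse in 21% |
| 6 | 1.20 | called worse in 25% |
| 5 | 1.29 | called worse in 31% |
| 4 | 1.39 | called worse in 38% |
| 12 | 0.88 | called better in 23% |
| 18 | 0.74 | called better in 34% |

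One case can be checked by hand. With medians of 12 and 6 months, put x = 2^(−t/12). The combination median solves (25/45)x + (20/45)x² = 0.5, so x = 0.606 and t = 8.7 months, against 12 months on nivolumab alone. No patient has been harmed, yet the log-rank statistic points against the combination in 71% of 3,000 simulated trials.

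**Step 5: comparison in all patients.** In the 4-month case of step 4, progression-free survival in 48 against 48 favours the combination. The hazard ratio is 0.78, 0.81 or 0.86 for an assumed median of 1.5, 2 or 3 months in non-responders. The two planned log-rank tests would tend to point in opposite directions.

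**The case against.** The best answer is that no harm can be shown from the documents. They give no rate of death in response and nothing about the added responders, so every size above is assumed. That is correct, and the figures are ranges for that reason.

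The shift may also be small. One or two deaths move the assumed median by 0.3 to 0.7 months. With a true median of 6 months, the 95% sampling range of the median is 3.4 to 9.9 months in 34 responders and 2.0 to 13.6 months in 12. Scans when clinically indicated (11.1.3) and stopping for clinical deterioration (5.3) should bring some progressions to light before death. Section 7.3.3 has deaths from progressive disease reported as grade 5 events, but that is an adverse event reporting rule and does not turn them into PD or PMD. These points reduce the problem and do not remove it.

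The 0.15 level belongs to the primary endpoint. At two-sided 5%, the combination is called worse in 2.6%, 4.0%, 4.6%, 6.7% and 10.5% of trials for added-responder medians of 8, 7, 6, 5 and 4 months, against a nominal 2.5%. The excess is then modest except in the extreme case.

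No formal rule uses the duration-of-response p-value. The interim and final rules rest on response rate, and the stopping sentence is general. That stands, and it limits the severity.

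Finally, follow-up ends 100 days after therapy, so a late death in response may not be recorded. That is true, but it limits progression-free and overall survival equally.

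**Conclusion.** The concern holds on the text. Section 13.4.1 omits death, its censoring rule takes in responders who die, and its test is confined to responders. No other section corrects either point. A progression-only definition can be legitimate if it is declared and labelled, but here it is unexplained and sits beside a progression-free survival definition that counts death.

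The size is conditional. Censoring deaths gives no bias if no responder dies without documented progression, and 0.3 to 2.6 months on an assumed 6-month median at 5% to 30% deaths. The selection effect may favour either arm, depending on how the added responders compare with the others. The reading of the text is certain; the practical consequence is not. The fault should be corrected, but it does not threaten the primary response-rate conclusion.

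**What to change.** Redefine duration of response as the time from first response to the earlier of documented progression or death from any cause. Censor only patients who are alive and progression-free, at their last assessment. Present responder Kaplan-Meier curves by arm as descriptive, and remove the log-rank test in responders. Labelling that test descriptive would remove much of the risk, but dropping it is cleaner because the plan gives it neither a level nor a side. Use progression-free survival, already planned in section 13.4.3, for the between-arm comparison of durability.

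As an option, add the proportion of all evaluable patients in response at the week-24 scan. Week 24 is 2 × 2.76 = 5.5 months, inside the minimum follow-up in section 13.1.3: "The final analysis will take place after all 48 evaluable patients in each group have been followed for at least 6 months". Non-responders, and patients without a scan showing continued response, would count as not in response. That rule is needed because section 5.4 sets no scan schedule after therapy ends.

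The cost is a change of wording and minor programming. Death dates are already required for progression-free and overall survival, so the core change needs no further data. Reported medians may be somewhat shorter, and one secondary p-value is lost.

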13.4.2 Survival Time

Survival time is defined as the time from randomization to death due to any cause. The distribution of survival time will be estimated using the method of Kaplan-Meier. The comparison of overall survival between two treatment arms will be based on the log-rank test.

13.4.3 Progression Free Survival

Progression free survival is defined as the time from randomization to the earliest

date of documentation of disease progression (PMD or PD) or death due to any cause. The distribution of progression-free survival will be estimated using the method of Kaplan-Meier. The comparison of progression-free survival between two treatment arms will be based on the log-rank test.

13.4.3.1 Adverse Events

All patients that have initiated treatment will be considered evaluable for assessing adverse event rate(s). The maximum grade for each type of adverse event will be recorded for each patient, and frequency tables will be reviewed for each arm to determine patterns. Additionally, the relationship of the adverse event(s) to the study treatment will be taken into consideration. The overall adverse event rates for Grade 3 or higher hematologic and non-hematologic adverse events at least possibly related to treatment will be compared between the two treatment groups using the Chi-square test (or Fisher's exact test if the data in the contingency table is sparse).

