2. BACKGROUND

2.1 Study Disease

Diffuse large B-cell lymphoma (DLBCL) remains the most common lymphoma worldwide and corresponded to 32.5% of a total of 596,476 non-Hodgkin lymphomas (NHL) diagnosed between 2008 and 2011 in the United States (Green *et al.*, 2010 and Dong *et al.*, 2002). Standard frontline treatment with chemo immunotherapy will cure about two thirds of these patients but a significant proportion will be either refractory to treatment or develop relapsed disease. Salvage treatment options in the relapsed/refractory settings are limited and most of these patients will unfortunately die from progressive disease.

Somatic alterations have been identified in DLBCL patients who fail to achieve durable remissions (Wilcox *et al.*, 2009) but the role played by the host immune system in this context is unknown. Checkpoint blockade therapy is used in a variety of cancers and works by modulating the host's immune system towards an effective anti-tumoral attack. Trials using programmed cell death protein 1 (PD-1) inhibitors in advanced hematological malignancies demonstrated remarkable activity in patients with Hodgkin lymphoma (HL) (Yang *et al.*, 2014, Yang *et al.*, 2015), leading to the recent regulatory approval of Nivolumab in the United Stated. Unfortunately, results in the DLBCL cohort were marginal and short lived (Yang *et al.*, 2012, Keir *et al.*, 2008).

Therefore, there is a critical need to extend the benefits of immunotherapy to patients with advanced DLBCL and other aggressive NHL. We hypothesize that the combination of two immunomodulatory agents will increase the anti-tumor activity compared to single-agent Nivolumab and improve clinical outcomes for this group of patients with no significant increase in toxicity.

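### The arms are compared on severe toxicity by a significance test alone, without an estimate of the difference or an interval, so a non-significant result would be weak evidence of no increase

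*Combined protocol and SAP*

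**What the plan says.** - **Hypothesis (section 2.1).** Two immunomodulatory agents are expected to raise anti-tumor activity over nivolumab alone and "improve clinical outcomes for this group of patients with no significant increase in toxicity". No acceptable excess is attached to this.
- **Objective (section 1.2.1).** Safety and tolerability of the combination is a secondary objective, worded as an assessment of the profile.
- **Between-arm analysis (section 13.4.3.1).** The outcome covers events of grade 3 and above, hematologic or not, judged at least possibly related. Their rates "will be compared between the two treatment groups using the Chi-square test", with Fisher's exact test for sparse tables. Level, sidedness, expected rates, an estimate of the difference and an interval are all absent. The population is everyone who started treatment.
- **Other safety provisions.** In the same section the maximum grade per event type is tabulated, and "frequency tables will be reviewed for each arm to determine patterns". Section 13.7 adds a stopping rule for grade 4 or higher non-hematologic events, applied to each group separately: 4 or more of the first 20 patients, then 20% of all patients.
- **Size (section 13.2.1).** "A maximum of 96 evaluable patients (48 in each group) will be accrued". With the allowance of 10 more for losses, the section adds: "Maximum projected accrual is 106 patients". The size was chosen for response.
- **Contrast with response (section 13.1.5).** Response gets exact 95% intervals in each arm and a test at one-sided 0.15.

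**The concern.** A test of difference can support a claim that toxicity rose. It cannot by itself support a claim that toxicity did not rise, because a non-significant result also arises when the sample is too small to show a real increase. The stated hypothesis is of the second kind, and the only tool offered for the comparison is of the first kind.

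The frequency tables and the stopping rule do not fill the gap. The tables are descriptive within each arm. The stopping rule compares each group with a fixed 20% and covers only grade 4 or higher non-hematologic events. Neither estimates the excess over nivolumab. A report that followed section 13.4.3.1 literally could give a p-value above 0.05 with nothing to show how large an increase the data still allow.

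**Working it through.** **Inputs.** From the documents: 48 evaluable patients per group (13.2.1), and at most 106/2 = 53 treated per group. Assumed, because the documents give neither: the rate on nivolumab (5% to 30%, with the combination at double that rate) and the level (two-sided 0.05, with one-sided 0.15 as an alternative). The nearest rate in the documents is in section 2.2.2.2.3: serious adverse events in 32 of 296 patients (11%) on nivolumab. That is a different outcome from the one tested here, so it serves only as orientation.

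**Step 1: reproduce the plan's own figure.** Section 13.1.3 states 80% power for response of 25% vs 45%, 48 per group, one-sided 0.15. Exact enumeration of the one-sided Fisher test gives 80.9%, so the method reproduces the design.

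**Step 2: power of the toxicity test.** With x events of n on nivolumab and y of n on the combination,

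z = (y/n - x/n) / sqrt[ p(1-p) × 2/n ], where p = (x+y)/(2n).

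The uncorrected chi-square test rejects at two-sided 0.05 when |z| > 1.96. Exact power is the sum, over all (x, y) that reject, of Bin(x; n, p1) × Bin(y; n, p2).

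| Nivolumab vs combination | Chi-square, n = 48, two-sided 0.05 | Fisher, n = 48, two-sided 0.05 | Chi-square, n = 53, two-sided 0.05 | Chi-square, n = 48, one-sided 0.15 |
|---|---|---|---|---|
| 5% vs 10% | 17% | 6% | 15% | 47% |
| 10% vs 20% | 29% | 18% | 30% | 65% |
| 15% vs 30% | 43% | 33% | 47% | 77% |
| 20% vs 40% | 59% | 49% | 63% | 88% |
| 30% vs 60% | 85% | 80% | 88% | 97% |

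At 11% vs 22%, two-sided 0.05 and n = 48, chi-square gives 32% and Fisher 21%. By the normal approximation, chi-square power at two-sided 0.05 passes 50% at a nivolumab rate of about 18%.

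**Step 3: what one non-significant result looks like.** Take 7/48 (14.6%) vs 15/48 (31.3%), a difference of 8/48 = 0.1667.

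- Pooled p = 22/96 = 0.2292. Standard error = sqrt(0.2292 × 0.7708 × 2/48) = 0.0858.
- z = 0.1667/0.0858 = 1.943; chi-square = 3.77; two-sided p = 0.052.
- Wilson 95% limits: 0.0725 to 0.2717 for 7/48, and 0.1995 to 0.4533 for 15/48.
- Newcombe lower limit: 0.1667 - sqrt[(0.3125 - 0.1995)² + (0.2717 - 0.1458)²] = 0.1667 - 0.1692 = -0.0025.
- Newcombe upper limit: 0.1667 + sqrt[(0.4533 - 0.3125)² + (0.1458 - 0.0725)²] = 0.1667 + 0.1588 = 0.3255.

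The test reports no significant difference at 0.05. The interval, -0.2 to +32.5 points, shows that the same data fit almost no change and also an excess of nearly a third of patients.

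**The case against.** The strongest reply is that section 2.1 is background prose. No section says the chi-square test decides whether toxicity has increased, and objective 1.2.1 makes no claim of equivalence. This is a phase 2 trial sized for response, and low power for a secondary safety comparison is ordinary. Tables and a stopping rule also exist. Much of this stands: the link between the hypothesis and the test is an inference, drawn because 13.4.3.1 is the only comparison that could address it.

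Four stronger readings are tempting but not supported:

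- **That the test has about 40% power, or that a doubling would more often than not be missed.** The documents state neither rate nor level. At two-sided 0.05 a doubling is detected more often than not once the nivolumab rate exceeds about 18%. At one-sided 0.15, chi-square power is already 65% from a rate of 10%.
- **That the plan is lenient on benefit and strict on harm.** No level is set for the toxicity test, so the asymmetry appears only if the reader supplies 0.05.
- **That this test drives the recommendation.** The final decision rule in 13.1.3 rests on response, "where the p-value < 0.15". Toxicity appears under other considerations for terminating the study, without reference to this p-value.
- **That nothing else watches safety.** The tables and section 13.7 do, although not as a comparison with nivolumab.

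None of this supplies an estimate of the difference. That gap remains whatever rate or level is assumed.

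**Conclusion.** The concern holds as a gap in estimation. The plan's only comparison of toxicity between arms yields a p-value, and at this size a non-significant p-value is weak evidence of no increase. Under the assumptions of 48 per arm and two-sided 0.05, exact chi-square power for a doubling ranges from about 17% to 85% as the nivolumab rate goes from 5% to 30%. Up to 53 treated per arm changes this only slightly, and a one-sided 0.15 level raises it. No single power figure is a property of the plan. The finding affects how a secondary objective is reported. It does not affect the primary analysis, the sample size or the response-based decision rule.

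**What to change.** In section 13.4.3.1, keep the outcome exactly as defined (grade 3 or higher, at least possibly related, hematologic and non-hematologic) and the population of all treated patients. Then add:

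1. The difference in proportions, combination minus nivolumab, with a two-sided 95% Newcombe or Miettinen-Nurminen interval.
2. A statement that the size of any increase is read from the interval, and that a non-significant p-value is not evidence of no increase.

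The chi-square or Fisher p-value can stay as supporting information. The cost is about two sentences and one line of code, with no extra patients or data. The only downside is a more cautious safety statement.
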